A random cross-sectional sample of parents and caregivers (hereafter referred to as "parents") will be selected to participate in a 5–10-minute self-administered survey conducted at 4-week intervals (see Table 3). Prospective parent participants will be identified using a sampling frame provided by schools, at the beginning of the school year, consisting of classroom, classroom size, and grade level. From the sampling frame, three classrooms within each school will be randomly selected. Within the randomly

selected classroom, teachers will distribute a survey invitation to all students. Average class size is 25 and we anticipate a 15% response rate per class, resulting in approximately 12 surveys per school or approximately 144 surveys per cluster; equating to 2,880 parent surveys during the 20-week period. Random samples of classrooms will be selected every 4-weeks with replacement using a randomization schedule generated by the study biostatistician, [name]. To increase generalizability, we will randomly select serial cross-sectional samples with replacement since serial samples will allow for greater representation given the likelihood of student absences on the day of recruitment (e.g., potential for individual students to be absent and/or classrooms to be quarantined due to COVID-19 exposure). All parents will be notified of the study and the possibility of receiving a survey invitation by school administrators at the beginning of the school year, with periodic reminders.

The primary outcome, diagnostic testing before and after implementation of the SASEA Hub will be examined using a mixed effects logistic regression with fixed effects for Time, SASEA Hub, and the interaction of Time x SASEA Hub. The mixed effects model will include a random component for school-level intercepts (to account for students nested within schools) and district-level intercepts (to account for schools nested in districts). Potential confounders will be controlled for in the model (e.g., baseline COVID-19 diagnostic testing and vaccination rates within communities encompassing schools, school size, race/ethnicity, % receiving free/reduced lunch).

FIDELITY

INTERVENTIONIST TRAINING AND TRACKING

All schools will be receiving the same SASEA Hub website as the intervention with minimal modifications based on their region. Region specific wastewater results and vaccine locations will be provided.

MEASURES TO MINIMIZE BIAS: RANDOMIZATION AND BLINDING

Because of the stepped wedge trial, all schools will be receiving the intervention (SASEA HUB). There is no randomization occurring in intervention rollout. As schools do not receive the website before the intervention, schools will not be in communication with other schools and will not find out about the website before the intervention is introduced to their campus.

STUDY INTERVENTION/EXPERIMENTAL MANIPULATION ADHERENCE

N/A

CONCOMITANT THERAPY

N/A

RESCUE THERAPY

N/A

STUDY INTERVENTION/EXPERIMENTAL MANIPULATION DISCONTINUATION AND PARTICIPANT DISCONTINUATION/WITHDRAWAL

DISCONTINUATION OF STUDY INTERVENTION/EXPERIMENTAL MANIPULATION

Because the website traffic and survey participation are voluntary, there will be no need to remove participants from the study.

PARTICIPANT DISCONTINUATION/WITHDRAWAL FROM THE STUDY

Participants are free to withdraw from participation in the study at any time upon request.

An investigator may discontinue a participant from the study for the following reasons:

- Significant study intervention non-compliance, unless varying compliance is an aspect of the study objectives
- Lost-to-follow up; unable to contact subject (see **Section 7.3, Lost to Follow-Up**)
- Any event or medical condition or situation occurs such that continued collection of follow-up study data would not be in the best interest of the participant or might require an additional treatment that would confound the interpretation of the study
- The participant meets an exclusion criterion (either newly developed or not previously recognized) that precludes further study participation

LOST TO FOLLOW-UP

There will be no follow up in this study. Participants are completing a one-time survey. Participants may decide to discontinue the survey at any time. Participants receiving notifications to the SASEA Hub website may also choose to discontinue the notifications.

STUDY ASSESSMENTS AND PROCEDURES

ENDPOINT AND OTHER NON-SAFETY ASSESSMENTS

No safety end point procedure was provided to participants since there was minimal risk in participating in a SASEA Hub school and completing the surveys.

SAFETY ASSESSMENTS

1. Physical risk management plan
 - a. We do not anticipate any physical risks from participating in this study.
2. Psychological risk management plan
 - a. Adverse Emotional Reaction: Following administration of screeners or surveys, if discomfort is evident. Significant discomfort will be study PI, [name], or her designee, and recommendation for continued monitoring by staff or for referral, as appropriate, for further evaluation and treatment will be made.
3. Social/political risk management plan
 - a. Adverse Community/Social impact from publication of study results: Significant rates of COVID-19 as well as other risk behaviors and psychiatric disorders occur in most ethnic groups. The specifics of the rates of these disorders and behaviors, their relationship to risk, protective, and resilience factors, and the effects of individual and environmental intervention remain to be determined. However, it seems unlikely that specific rates or characteristics of these factors in historically marginalized school communities in San Diego County or differences as compared to other groups will lead to stigmatization. Nevertheless, we plan to take the following steps to minimize this risk:
 - b. Ongoing community feedback to school communities about the nature, purposes, and results of the study. This will afford an opportunity for community feedback on issues that might represent potential risk of stigmatization prior to publication of results.
4. Confidentiality risk management plan
All identifiable PHI data will be stored on a secure REDCap server and shared with the CDCC using appropriate protocols. Paper documents and digital recorders containing names and other identifying information (i.e., paper consent forms, focus group transcripts) will be kept in a locked file drawer in a locked office. All digital files will be deleted after transcription. Transcripts will be de-identified and kept on a password protected computer.

Assessment of adverse events. PI, [name] MSPH, or her designees, who will constitute the committee responsible for monitoring the safety of this study, executing the Data and Safety Monitoring Plan (DSMP), and complying with the reporting requirements. All Serious Adverse Events will be reported to the UCSD IRB and to NIH within two business days.

ADVERSE EVENTS AND SERIOUS ADVERSE EVENTS

DEFINITION OF ADVERSE EVENTS

Mild adverse event (AE is transient and usually self-limited, requires no more than minimal intervention, monitoring, or treatment, does not interfere with the participant's daily activities, usually does not require discontinuation from the study).

Moderate adverse event (AE may or may not be transient and self-limited, requires more than minimal intervention, monitoring, or treatment, interferes with daily activities, usually does not require discontinuation from the study).

DEFINITION OF SERIOUS ADVERSE EVENTS

Severe adverse event (AE usually not transient and self-limited, requires significant intervention, monitoring, or treatment, any AE resulting in hospitalization, prolongation of existing hospitalization, or significant disability/incapacity).

Life-threatening adverse event, persistently disabling adverse event, or a congenital anomaly/birth defect.

Fatal adverse event.

CLASSIFICATION OF AN ADVERSE EVENT

N/A

2.4.1.1 SEVERITY OF EVENT

Mild adverse event (AE is transient and usually self-limited, requires no more than minimal intervention, monitoring, or treatment, does not interfere with the participant's daily activities, usually does not require discontinuation from the study).

Moderate adverse event (AE may or may not be transient and self-limited, requires more than minimal intervention, monitoring, or treatment, interferes with daily activities, usually does not require discontinuation from the study).

Severe adverse event (AE usually not transient and self-limited, requires significant intervention, monitoring, or treatment, any AE resulting in hospitalization, prolongation of existing hospitalization, or significant disability/incapacity).

Life-threatening adverse event, persistently disabling adverse event, or a congenital anomaly/birth defect.

Fatal adverse event.

2.4.1.2 RELATIONSHIP TO STUDY INTERVENTION/EXPERIMENTAL MANIPULATION

Related – The AE is known to occur with the study procedures, there is a reasonable possibility that the study procedures caused the AE, or there is a temporal relationship between the study procedures and

the event. Reasonable possibility means that there is evidence to suggest a causal relationship between the study procedures and the AE.

Not Related – There is not a reasonable possibility that the study procedures caused the event, there is no temporal relationship between the study procedures and event onset, or an alternate etiology has been established.

EXPECTEDNESS

The likelihood of the incidence of the occurrence of each adverse event during a participant's involvement in the study is estimated using the following categories:

Likely: incidence equal to or greater than 10%

Less Likely: incidence equal to or greater than 1% to less than 10%

Rare: incidence less than 1%

1. Physical Risk: rare, no biological samples will be collected from human subjects in this study
2. Psychological Risk: Adverse emotional reaction to the information collected in screeners or surveys. This includes an adverse emotional reaction to reporting substance use, related morbidity, or other associated problems (mild, rare).
3. Social/Political Risk: Adverse community/social impact from publication of study findings (moderate, rare).
4. Legal Risk: Lawsuits arising from the testing intervention (moderate, rare).
5. Confidentiality Risk: Loss of confidentiality in any of the studies, but particularly those obtaining Identified PHI (private health information) (moderate, rare).
6. Other Risks: None

TIME PERIOD AND FREQUENCY FOR EVENT ASSESSMENT AND FOLLOW-UP

[name] MSPH, or her designees, who will constitute the committee responsible for monitoring the safety of this study, executing the Data and Safety Monitoring Plan (DSMP), and complying with the reporting requirements. All Serious Adverse Events will be reported to the UCSD IRB and to NIH within two business days.

2.4.2 ADVERSE EVENT REPORTING

[name] MSPH, or her designees, who will constitute the committee responsible for monitoring the safety of this study, executing the Data and Safety Monitoring Plan (DSMP), and complying with the reporting requirements. All Serious Adverse Events will be reported to the UCSD IRB and to NIH within two business days.

2.4.3 SERIOUS ADVERSE EVENT REPORTING

[name] MSPH, or her designees, who will constitute the committee responsible for monitoring the safety of this study, executing the Data and Safety Monitoring Plan (DSMP), and complying with the reporting requirements. All Serious Adverse Events will be reported to the UCSD IRB and to NIH within two business days.

2.4.4 REPORTING EVENTS TO PARTICIPANTS

N/A

2.4.5 EVENTS OF SPECIAL INTEREST

N/A

2.4.6 REPORTING OF PREGNANCY

N/A

2.5 UNANTICIPATED PROBLEMS

2.5.1 DEFINITION OF UNANTICIPATED PROBLEMS

This protocol uses the definition of Unanticipated Problems as defined by the Office for Human Research Protections (OHRP). OHRP considers unanticipated problems involving risks to participants or others to include, in general, any incident, experience, or outcome that meets all of the following criteria:

- Unexpected in terms of nature, severity, or frequency given (a) the research procedures that are described in the protocol-related documents, such as the Institutional Review Board (IRB)-approved research protocol and informed consent document; and (b) the characteristics of the participant population being studied;
- Related or possibly related to participation in the research (“possibly related” means there is a reasonable possibility that the incident, experience, or outcome may have been caused by the procedures involved in the research); and
- Suggests that the research places participants or others at a greater risk of harm (including physical, psychological, economic, or social harm) than was previously known or recognized.

2.5.2 UNANTICIPATED PROBLEMS REPORTING

[The investigator will report unanticipated problems (UPs) to the reviewing Institutional Review Board (IRB) and to the Data Coordinating Center (DCC)/lead principal investigator (PI). The UP report will include the following information:

[name] MSPH, or her designees, who will constitute the committee responsible for monitoring the safety of this study, executing the Data and Safety Monitoring Plan (DSMP), and complying

with the reporting requirements. All Serious Adverse Events will be reported to the UCSD IRB and to NIH within two business days.

2.5.3 REPORTING UNANTICIPATED PROBLEMS TO PARTICIPANTS

N/A

3 STATISTICAL CONSIDERATIONS

3.1 STATISTICAL HYPOTHESES

- Primary Endpoint(s):

For the primary outcome, we hypothesize that diagnostic testing among household members of students will be higher in the control arm. We will test this hypothesis using self-administered survey data. Survey participants will be asked if they (1)have learned of any positive cases at the school site in the previous 14 days, and (2)whether or not they and their household members accessed a diagnostic test as a result of that notification.

- Secondary Endpoint(s):

N/A

3.2 SAMPLE SIZE DETERMINATION

Power was computed for a randomized stepped wedge design with 48 schools, 4 clusters (12 schools per cluster), and 5 steps with 1 cluster per step (or 4-week interval) based on diagnostic testing uptake in response to a positive environmental signal (see 1, responsive testing). Power is based on the primary outcome, on-site COVID-19 diagnostic testing uptake in response to a positive environmental signal in schools (see section A.4.1 and C.5.2). Published studies on the uptake of COVID-19 diagnostic testing among school-aged children and their household members in the presence of environmental surveillance are non-existent. We relied on testing rates observed in San Diego County schools during the latter half of the 2020-2021 academic year. Assuming a baseline COVID-19 testing rate of 2%, intra-class correlation $ICC=0.10$, Type I error rate of 0.05, and an average of 500 staff/students per school, we will have more than 80% power to detect a minimal difference of 0.06% in weekly testing uptake (2.0% pre SASEA-SNAP vs. 2.6% post SASEA-SNAP). Using similar assumptions for the secondary outcome, COVID-19 diagnostic testing uptake within household members of students, we will have over 80% power to identify a minimal detectable difference of 2.8% in testing uptake with a serial cross-sectional sample of 2,880 parents (2.0% pre SASEA-SNAP vs. 4.8% post SASEA-SNAP). Power was calculated in STATA 16.1 using a method described by Hemming and Girling

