1 PROTOCOL SUMMARY

Protocol Title	Safer at School Early Alert Hub
Principal Investigator	[name]
Study Sites	University of California, San Diego
Study Activation Date	September 19, 2022
Planned Accrual	Total number of participants - 971
Planned Accrual Period	September 19, 2022 to December 17, 2022
Planned Duration	Data collection period: September 19, 2022 to December 17, 2022 Intervention period: October 3, 2022 to March, 2023
Study Design	Create the Safer at School Early Alert School Hub (SASEA Hub), a school-based environmental surveillance dashboard and diagnostic testing resource hub with an accompanying toolkit for rapid community tailoring to improve COVID-19 testing uptake in vulnerable and underserved communities using a Community Based Participatory Research (CBPR) framework and the Consolidated Framework for Implementation Research (CFIR). We will evaluate the ability of the saseahub.org to increase child and household diagnostic testing uptake via a step-wedge trial, with schools rotated onto the intervention arm (i.e., given access to the saseahub.org) at 2-week intervals. All schools will rotate into the intervention by the Thanksgiving holiday.

Study Objectives	
Aim 1: Create the SASEA Hub, a school-based environmental surveillance dashboard and diagnostic testing resource hub with an accompanying toolkit for rapid community tailoring to improve COVID-19 testing uptake in vulnerable and underserved communities using a Community Based Participatory Research (CBPR) framework and the Consolidated Framework for Implementation Research (CFIR).
 
Aim 2: Assess SASEA Hub's (intervention's) potential to increase diagnostic testing uptake and identify more asymptomatic cases than schools. We will assess this aim through a randomized stepped wedge cluster trial design. The primary outcome will be testing uptake within the past 14-day period, assessed through the SASEA bi-weekly community survey.
 
Aim 3: Assess SASEA Hub's ability to increase risk mitigation behaviors (masking, physical distancing, increased hand hygiene) when the Hub notifies schools of a change in county level COVID-19 case rates or county level wastewater levels

Treatment Description	Intervention – receive access to the community tailored SASEA Hub website
Inclusion Criteria	Parent of a child or staff member attending one of 26 SASEA participating schools

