Exclusion Criteria	All non SASEA school participating individuals or students of SASEA participating schools
Study Outcomes	Primary outcome – The primary study endpoint will be student diagnostic testing uptake in the previous 14-days, measured using household surveys distributed at 2-week intervals.

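### The power of over 80% in Section 3.2 belongs to a different design and different outcomes from those in the Protocol Summary, and a 0.6-point difference is printed as 0.06%

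*Combined protocol and SAP*

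**What the plan says.** **Section 3.2.** Power is stated for one design: "Power was computed for a randomized stepped wedge design with 48 schools, 4 clusters (12 schools per cluster), and 5 steps", with 4-week steps. Two outcomes are covered.

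- Outcome treated as primary: "Power is based on the primary outcome, on-site COVID-19 diagnostic testing uptake in response to a positive environmental signal in schools". The inputs are a 2% baseline, ICC 0.10, type I error 0.05 and 500 staff and students per school. The claim is more than 80% power for a "minimal difference of 0.06% in weekly testing uptake (2.0% pre SASEA-SNAP vs. 2.6% post SASEA-SNAP").
- Outcome treated as secondary: testing among students' household members. The claim is over 80% power for 2.0% vs 4.8% with a "serial cross-sectional sample of 2,880 parents".

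**Protocol Summary.** Planned accrual is "Total number of participants - 971". Eligibility is "Parent of a child or staff member attending one of 26 SASEA participating schools". Rollout is described as "with schools rotated onto the intervention arm (i.e., given access to the saseahub.org) at 2-week intervals". The endpoint is: "The primary study endpoint will be student diagnostic testing uptake in the previous 14-days, measured using household surveys distributed at 2-week intervals". The Objectives and Endpoints table limits it to children.

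**Elsewhere.**

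- Sections 2.4, Justification for Intervention, Strategies for Recruitment and Retention, and Administration and/or Dosing keep 48 sites. The detailed inclusion criteria say 50 schools.
- Administration and/or Dosing and Section 3.3 keep 2,880 surveys.
- Section 3.1 names household-member testing as primary.
- Section 3.4.2 assesses the primary outcomes from weekly surveillance data as well as parent surveys.
- Section 4.3 records a single protocol version, so all of this is current text.

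**The concern.** Neither outcome powered in Section 3.2 is the child survey endpoint in the Summary and the objectives table. The school count, number of observations and step length also differ. A reader therefore cannot tell what effect the trial can detect on the primary endpoint named in the Summary.

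A null result from 971 surveys could be reported as coming from a trial with over 80% power for 0.6 or 2.8 points. The printed 0.06% adds a tenfold error in the only effect size given for the outcome Section 3.2 calls primary.

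**Working it through.** **Misprint.** 2.6% − 2.0% = 0.6 percentage points. A true difference of 0.06 points (2.00% vs 2.06%) would have only about 6-7% power under the stated design, so 0.6 is what was powered.

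**Method.** Cross-sectional stepped wedge with a random school intercept and fixed period effects. With I schools, T periods and m observations per school-period:

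Var = I·e·(e + T·t) / [(I·U − W)·e + (U² + I·T·U − T·W − I·V)·t]

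- t = ICC × s² and e = (1 − ICC) × s²/m.
- U is the number of exposed school-periods. W sums the squared exposed counts over periods, and V sums them over schools.
- s² is either the average of p(1−p) at the two rates (averaged) or p(1−p) at baseline (baseline-only). Section 3.2 does not say which was used.
- Power is two-sided at 0.05, an assumption because sidedness is not stated.

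**Section 3.2's own figures** (I = 48, T = 5, 12 schools per sequence). U = 120, W = 4,320, V = 360, so the bracket is 1,440·e + 4,320·t.

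- 500 per school-period, 2.0% vs 2.6%, averaged: s² = 0.022462, t = 0.0022462, e = 0.0000404, SE = 0.00150. Power = Φ(0.006/0.00150 − 1.96) = 98% (99% baseline-only). The claim reproduces, provided 500 people per school are observed in every period.
- 12 per school-period (48 × 12 × 5 = 2,880), 2.0% vs 4.8%, averaged: s² = 0.032648, SE = 0.01119, power = Φ(2.503 − 1.96) = 71%. Baseline-only: SE = 0.00867, power 90%. The variance choice alone decides whether this claim reproduces two-sided.

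**The Summary's design.**

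- 19 September to 17 December 2022 is 90 days, or 6.4 two-week periods; 5 to 7 are used.
- Steps every 2 weeks from 3 October fall on 3, 17 and 31 October and 14 November: four steps before Thanksgiving.
- Assumptions: 26 schools split 7/6/7/6, 971 surveys spread evenly, ICC 0.01-0.10, and a 2% baseline borrowed from the on-site calculation. The documents give no 14-day child rate.

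Central case: T = 6, ICC 0.10, m = 971/(26 × 6) = 6.2. U = 92, W = 1,970, V = 358, so the bracket is 422·e + 1,688·t.

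- 2.0% vs 4.8%, averaged: t = 0.003265, e = 0.004721, SE = √[26 × 0.004721 × 0.024311 / 7.5036] = 0.0199. Power = Φ(1.404 − 1.96) = 29%.
- 2.0% vs 4.8%, baseline-only: SE = 0.01545, power = Φ(1.812 − 1.96) = 44%.
- 2.0% vs 2.6%: 6.5% and 6.7% (both tails counted).
- Detectable difference at 80% power solves d = (1.960 + 0.842) × SE(d): 6.95 points averaged; 2.802 × 0.01545 = 4.33 points baseline-only.

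Ranges over 5-7 periods and ICC 0.01-0.10, with 26 schools and 971 surveys:

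| Quantity | Averaged | Baseline-only |
|---|---|---|
| Power, 2.0% vs 2.6% | 6-7% | 7% |
| Power, 2.0% vs 4.8% | 27-37% | 41-55% |
| Power, 2% vs 12% | 93-99% | >99.9% |
| Detectable difference, 2% base | 5.7-7.5 points | 3.8-4.6 points |
| 5% base | 7.5-9.6 | 5.8-7.1 |
| 10% base | 9.4-11.8 | 8.0-9.8 |
| 20% base | 11.6-14.3 | 10.7-13.0 |

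**Source of the loss.**

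| Variation | Difference | Averaged | Baseline-only |
|---|---|---|---|
| 26 schools, 500 per school-period | 0.6 points | 81-90% | 86-93% |
| 48 schools, 971 surveys | 2.8 points | 28-38% | 42-57% |
| 26 schools, 2,880 surveys | 2.8 points | 60-75% | 82-92% |

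The survey count (971/2,880 = 0.337), not the school count, drives the loss.

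**The case against.** Five points can be made for the plan.

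1. **Section 3.2 is not shown to be miscalculated for its own design.** The on-site claim reproduces, and the household claim does under one variance choice. The only slip in arithmetic is the misprint, and both rates stand beside it. This is right: the main defect is a mismatch between sections.
2. **The consequence depends on which text governs.** If weekly surveillance remains a primary data source, as Section 3.4.2 allows, 26 schools with 500 observed per period keep over 80% power for 0.6 points. This stands, and it is why the figures for the Summary's design are conditional. That endpoint is survey-reported, however, and no power is given for it.
3. **971 appears only in the Summary.** The recruitment text implies about 20 surveys per site at a 25% response; Section 3.3 implies about 12 at 15%. For 26 schools over 5-7 rounds that is 1,560 (26 × 5 × 12) to 3,640 (26 × 7 × 20) surveys. Power for 2.8 points is then 45-71% (averaged) or 66-90% (baseline-only) at ICC 0.10. The yields need reconciling too, but these totals are not the planned accrual.
4. **The 971 may include staff without a child outcome.** If 30% were such staff (an assumption; no share is given), power for 2.8 points falls to about 22% or 34% in the central case. Counting all 971 favours the plan.
5. **The approximation is rough.** At 2% and 6.2 surveys per school-period, about 0.12 events are expected per cell. The planned analysis is a mixed logistic model with a time-by-Hub interaction, district intercepts and covariates. The figures show the scale and are not the trial's exact power.

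The statement under Measures to Minimize Bias that rollout is not randomised also conflicts with the randomised design powered. It is a separate matter and does not alter this point.

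**Conclusion.** The concern holds and must be fixed. Two parts rest on the text alone. No power or detectable difference is stated for the Summary's design or its 14-day child survey endpoint, and 0.06% should read 0.6 percentage points.

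The size depends on the Summary design being current and on the assumptions listed above, chiefly the borrowed 2% baseline. Under them, neither difference named in Section 3.2 reaches 80% power with 971 surveys under any setting tried. The trial would still detect a large effect: a 10-point rise from 2% has at least 93% power.

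**What to change.** 1. Reconcile the number of schools, sample size, survey yield, step length, data source and primary endpoint. The places are the Protocol Summary, the Objectives and Endpoints table, Section 2.4, Justification for Intervention, Inclusion Criteria, Strategies for Recruitment and Retention, Administration and/or Dosing, and Sections 3.1, 3.2, 3.3 and 3.4.2.
2. Recompute Section 3.2 for the reconciled design. State and justify the 14-day baseline rate, and state the variance convention, the sidedness and the observations per school-period. Count only respondents who contribute a child outcome.
3. Replace the two claims of over 80% power with the resulting power or detectable difference. If the Summary design is confirmed, report the detectable difference under both variance conventions. The 5.7-7.5 and 3.8-4.6 points here are illustrative at a 2% baseline until that is done.
4. Correct 0.06% to 0.6 percentage points.

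The cost is reconciling existing text, one recalculation and some rewording. Enrolment and data collection do not change. If the Summary design stands, the stated power becomes less favourable.
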